Diagnosis and main criteria for inclusion	Osteosarcoma with 1) metastatic or recurrent disease and 2) indicator lesion(s) avid on ^{99m} Tc-MDP bone scan.
Study design	The study design is a 3+3 Phase I dose escalation (N=3/cohort) with expansion at highest safe dose (N=6); if 75kBq is 2/3 DLT, the dose -1 (50kBq/kg) is the MTD
Type of control	Uncontrolled study (i.e. no placebo or control group)
Number of subjects	Dose escalation N=14; dose expansion N=6 ;total= 20
Plan for statistical analysis	
Primary objective: Determine maximum tolerated or recommended dose of monthly 223-radium dichloride in patients with recurrent or metastatic osteosarcoma. Comparison of safety and toxicity of 50, 75, and 100 kBq 223-radium dichloride /kg will be made.
 
Secondary Objectives: Analysis change in objective measurements of alkaline phosphatase pre , before dose 4 (mid study) and at end of study (after dose 6) vs change in SUV of for PET- scans (¹⁸FDG and /or ¹⁸FNa) and of SPECT CT for ^{99m}Tc-MDP. Changes in uptake will be analyzed for dose response effects (between groups) and pre vs mid study and end of study (within group)

List of abbreviations

AE	Adverse Event
ALP	Alkaline Phosphatase
ALSYMPCA	Alpharadin in Symptomatic Prostate Cancer
ALT	Alanine Aminotransferase
ANC	Absolute Neutrophil Count
AST	Aspartate Aminotransferase
BPI-SF	Brief Pain Index (Short Form)
BSoC	Best Standard of Care
CBC	Complete Blood Count
CRO	Clinical Research Organization
CRPC	Castration Resistant Prostate Cancer
CT	Computed tomography
CTCAE	Common Terminology Criteria for Adverse Events; version 4.03
DK	Decay Correction Factor
EBRT	External Beam Radiation Therapy
ECOG	Eastern Co-operative Oncology Group
eCRF	Electronic Case Report Form
EU	European Union
GCP	Good Clinical Practice
GCL	Global Clinical Leader
GMP	Good Manufacturing Practice
HRPC	Hormone Resistant Prostate Cancer
IB	Investigator Brochure
ICF	Informed Consent Form
ICH	International Conference on Harmonization
IDMC	Independent data monitoring committee
IEC	Independent Ethics Committee
IRB	Institutional Review Board
IV	Intravenous
IxRS	Interactive Voice/Web Response System (IVR/IVRS)
kBq	KiloBecquerel; SI Unit of Radioactivity
kg	Kilogram
LHRH	Luteinizing-Hormone-Releasing Hormone; also known as Gonadotropin-Releaseing Hormone (GnRH)
mCi	Millicuries
MedDRA	Medical Dictionary for Regulatory Activities
mL	Milliliter
MRI	Magnetic Resonance Imaging
NCI	National Cancer Institute
NYHA	New York Heart Association

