1.1 Background

Ra-223 dichloride is potentially a very low toxicity and high efficacy targeted agent for osteosarcoma, an osteoblastic bone-forming tumor. Because of low marrow toxicity of this radiopharmaceutical, knowledge of the MTD in this patient population is needed to develop future protocols. Use of Ra-223 dichloride in osteosarcoma should reduce the morbidity of therapy and mortality from metastases. The goal of this initial study is to determine the safety of escalating doses of monthly $^{223}\text{RaCl}_2$ in osteosarcoma patients with osteoblastic bone-forming metastases until MTD or a dose 100 kBq/kg dose is reached (whichever is first). Ra-223 dichloride will be given monthly and side effects of this bone-targeted therapy on monthly blood counts and alkaline phosphatase will be determined. After 3 and 6 doses patients will have imaging to compare $^{99\text{m}}\text{TcMDP}$ uptake to baseline and other imaging as clinically indicated including ^{18}F -FDG PET-CT, Na^{18}F and/ chest CT. Evaluations will include anatomic imaging (CT or MRI) of all sites of disease along with chest CT at baseline and restaging for all patients to allow for assessment of RECIST progression. RECIST progression will determine progressive disease regardless of other imaging. If well tolerated at the MTD, an additional 6 patients will be studied to better define toxicity and obtain data to support future investigation of Ra-223 dichloride with other agents and modalities (e.g. other drugs, surgery or external beam RT) for improved treatment of osteosarcoma.

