beforehand and given suitable personal protection equipment (i.e. universal blood and body fluid precautions - especially when handling ashes containing potentially radioactive bone fragments. Calculations and the rationale for radiation dose estimates are available upon request (see investigators Brochure).

Definition of Dose-Limiting Toxicities (DLTs):

Toxicities will be graded in severity according to the guidelines outlined in the NCI Common Terminology Criteria for Adverse Events (CTCAE) version 4.0 (publish date 28-May-2009). Dose-limiting toxicities include all adverse experiences that are related to study medication, and clearly not related to disease progression or intercurrent illness.

Based on prior experience with other bone seeking radiopharmaceuticals and Ra-223 dichloride in prostate cancer patients, the expected dose limiting toxicity (DLT) will be hematologic. Lymphopenia is common in patients with bone metastases and will be monitored, but not considered a DLT in this protocol. Any grade 4 anemia, any grade 4 neutropenia for >7 days or grade 4 neutropenia with fever (a single temperature greater than 38.3°C or a sustained temperature of $\geq 38^\circ\text{C}$ for more than one hour) and grade 3 or 4 thrombocytopenia with clinically significant bleeding will be dose limiting. Grade 3 non-hematologic toxicities except for nausea, emesis or diarrhea that are controlled with maximal medical management within 72 hours will be considered dose-limiting. DLTs will only be monitored during the first 6 weeks of treatment. Ongoing toxicity that causes a delay of more than 2 weeks in starting the next cycle will also be dose-limiting if it occurs during the first cycle.

Dose Modification and Escalation

Every effort should be made to administer the full dosing regimen of Ra-223 dichloride. Adjustment of dose level is not permitted.

- A minimum of 3 patients initially will be enrolled at the first dose level.
- If at least 2 patients are observed to have a dose-limiting toxicity (DLT), the MTD will have been exceeded and no further patients will be enrolled at this dose level or at any higher dose level. The prior dose level is defined as the MTD (unless only 3 patients have been treated at that level, in which case it is the tentative MTD).
- If 0 of the 3 patients are observed to have DLT during the DLT assessment period, the dose level is escalated one step for the next cohort of 3 patients, and the process continues as above.

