- If exactly 1 of the 3 patients treated show DLT during the DLT assessment period, 3 additional patients are treated at the current dose level.
- If none of these additional 3 patients show DLT during the DLT assessment period, the dose level is escalated for the next cohort of 3 patients, and the process continues as above; otherwise, the prior dose level is defined as the MTD (unless only 3 patients have been treated at that level, in which case it is the tentative MTD).
- A tentative MTD becomes final when a total of 6 patients are treated with less than 2 showing DLT.
- If 2 of the first 3 patients have hematologic DLT, then next cohort will be dose level -1.

Study visits during the treatment period should occur at 4 weeks intervals (within a window of +/- 7 days). **Dosing delays** may be instituted under the following circumstances:

Disease progression:

The Investigator should delay cytotoxic chemotherapy, other systemic radioisotope, hemibody external radiotherapy or other investigational drug until the follow-up period. If such treatments have to be given during the treatment period, further study drug administrations must be discontinued. Patients with disease progression may continue other treatment at the Investigator's discretion.

Myelosuppression:

Treatment-related changes in hematology parameters may occur.

- Blood transfusion is acceptable between study drug administrations. Use of biologic response modifiers, such as G-CSF or GM-CSF, is allowed in the management of acute toxicity.
- If myeloid growth factors are required for the management of acute toxicity this event should be considered a DLT.

Gastrointestinal events:

Diarrhea should be treated as per local practice. A further dose of study medication should not be given before diarrhea is recovered to CTCAE v4.03 Grade 2 or baseline levels.

Nausea or vomiting should be treated as per local practice. A further dose of study medication should not be given before nausea or vomiting is recovered to CTCAE v.4.03 Grade 2 or baseline levels.

For any grade 3 hematologic toxicity for >14 days, study drug administrations must be discontinued (grade 4 events of anemia and neutropenia >7 days are dose-limiting).

Spinal Cord Compression:

If the patient experiences spinal cord compression during the treatment period, the patient should be treated for the event, and this will be considered disease progression.

Surgical Intervention:

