8.1 Analysis sets

Safety monitoring rule

- Should DLTs occur in more than two patients at any time during the dose expansion phase clinical personnel and study investigators will meet and assess the attribution, severity and nature of the DLTs. No additional patients will be accrued until the data is reviewed and a decision is made to continue at the current dose or to de-escalate the prior dose as the dose for the expansion phase. This review and decision will be documented in writing.

Monitoring of alkaline phosphatase

- Alkaline phosphatase, a biomarker associated with osteosarcoma metastases, will be determined monthly before administration of each dose of Ra-223 dichloride. The trend of improvement (or not) will be analyzed for a particular patient and number of patients in a cohort with improvement as a function of dose # will be analyzed.

Imaging

- Nuclear Medicine Studies will use commercially available ^{99m}Tc , ^{18}F Fluorodeoxyglucose and sodium ^{18}F Fluoride to image indicator lesions. The trend of improvement (or not) in ^{99m}Tc -MDP on SPECT CT, ^{18}F FDG-PET-CT SUV, or Na^{18}F SUV will be compared for study entry vs after dose #3 and study entry vs after dose #6 and after dose #3 vs after dose #6 will analyzed for a particular patient and number of patients in a cohort with improvement after dose #3 and dose #6 will be analyzed.
- Analysis of lung metastases. Up to 3 measurable (1 cm or larger) indicator lesions seen on chest CT may be described at study entry and compared after dose #3 and dose #6. RECIST criteria (>20% increase in size) will be used as criteria for progression. Any change <20% or if size is <1 cm will not be used for “off study” progression criteria.
- RECIST progression will determine progressive disease regardless of other imaging.

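### The escalation rules do not properly handle closure of the 50 kBq/kg starting level: on two routes no cohort opens at 25 kBq/kg, yet read literally that untreated level becomes the MTD

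*Combined protocol and SAP*

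**What the plan says.** Table 1 (Section 4) sets the starting level at 50 kBq/kg and lists level -1 at 25 kBq/kg, with a dash in place of a number of patients. The rules are in the bullets under Dose Modification and Escalation, within Section 6.2.9.

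- Closure for two or more DLTs of any type: "If at least 2 patients are observed to have a dose-limiting toxicity (DLT), the MTD will have been exceeded". The level below is then the MTD, or a tentative MTD if only 3 patients were treated there.
- Closure after one DLT in the first 3 and at least one in the next 3: "otherwise, the prior dose level is defined as the MTD (unless only 3 patients have been treated at that level", with the same tentative label for that exception.
- Confirmation: "A tentative MTD becomes final when a total of 6 patients are treated with less than 2 showing DLT".
- Level -1: "If 2 of the first 3 patients have hematologic DLT, then next cohort will be dose level -1".

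DLTs need not be hematologic. The DLT definition in the same section says: "Grade 3 non-hematologic toxicities except for nausea, emesis or diarrhea that are controlled with maximal medical management within 72 hours will be considered dose-limiting".

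The dose lists in Sections 6.2.2 and 6.2.7 contain 50, 75 and 100 kBq/kg but not 25. The text and volume formula in Section 6.2.7 are fixed at 50 kBq/kg.

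**The concern.** The plan foresees that the starting level may fail: it names a lower level and has a bullet that sends patients to it. But that bullet looks only at the first 3 patients and only at hematologic DLTs, while the closing rules count DLTs of any type and among up to 6 patients. Some closures of 50 kBq/kg therefore never reach the level -1 bullet. Nothing in the plan explains why two hematologic DLTs in 3 patients should lead to a test of 25 kBq/kg while two in 6 should not.

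On those routes the general closing rule still points to the level below. Its exception for a tentative MTD was written for a level with 3 patients, whereas level -1 has none. At stake is the primary objective, the maximum tolerated or recommended dose. On this branch the rule would name a dose with no DLT data from this trial.

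**Working it through.** **The plan's own total.** Table 1 gives 3 + 3 + 8 = 14 in escalation, plus 6 in expansion = 20, which matches the Synopsis. None of the 20 is allotted to level -1.

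**Routes that close 50 kBq/kg before any escalation.**

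| Route | First 3 patients | Next 3 | Level -1 bullet fires? | Treated at 25 kBq/kg |
|---|---|---|---|---|
| 1 | 1 DLT, any type | at least 1 DLT | No: at most one of the first 3 has a DLT | 0 |
| 2 | 2 or more DLTs, fewer than 2 hematologic | none enrolled | No | 0 |
| 3 | 2 or more hematologic DLTs | none enrolled | Yes | cohort opened |

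Route 1 misses the bullet even if every DLT is hematologic. On routes 1 and 2 the level below is 25 kBq/kg. Zero patients is not 3 patients, so on the literal text it is the MTD and not a tentative one. The confirmation bullet applies only to a tentative MTD.

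**How often.** The documents give no DLT rate at 50 kBq/kg in osteosarcoma, so the rate p is assumed. So is h, the share of DLTs that are hematologic. Patients are taken as independent, q = 1 - p, and the level -1 trigger is read as at least 2 of 3.

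- P(close) = 1 - [q³ + 3pq²·q³]
- Route 1 = 3pq²·(1 - q³)
- Route 2 = 3p²q·(1 - h²) + p³·[(1 - h)³ + 3h(1 - h)²]

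Worked case, p = 0.05 and h = 0.5:

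- Route 1 = 0.135375 × 0.142625 = 0.0193
- Route 2 = 0.007125 × 0.75 + 0.000125 × 0.5 = 0.0054
- Sum = 0.0247

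| p | P(close) | Routes 1+2, h = 1 | h = 0.8 | h = 0.5 |
|---|---|---|---|---|
| 2% | 0.46% | 0.34% | 0.38% | 0.43% |
| 5% | 2.66% | 1.93% | 2.19% | 2.47% |
| 10% | 9.39% | 6.59% | 7.57% | 8.66% |
| 20% | 29.1% | 18.7% | 22.3% | 26.3% |

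With h = 1, route 2 vanishes and that column is route 1 alone. With h = 0, every closure is uncovered, so P(close) is the ceiling. Reading the trigger as exactly 2 would add p³h³, at most 0.0125 percentage points at p = 5% and 0.1 at p = 10%.

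If all DLTs are hematologic, route 1 is 74% of closures at p = 2%, 70% at 10% and 57% at 30%. The bullet therefore misses the commoner route at low and moderate rates.

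**Patients needed if level -1 is tested.** At most 6 at 50 kBq/kg + 6 at 25 kBq/kg + 6 in expansion = 18, before replacements under Section 5.2.3.

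**The case against.** The strongest reply concerns the reading. If the exception for 3 patients is taken by its purpose, as meaning not yet 6, then 25 kBq/kg is a tentative MTD and needs 6 patients with fewer than 2 DLTs. Alternatively, the prior level may mean one already given in this trial, in which case the rule is simply silent. Both readings are reasonable, and they limit the claim: that an untested MTD is declared holds only on the literal text. Neither closes the gap. On the first, the level -1 bullet still does not fire and 25 kBq/kg is still not in the dose lists. On the second, there is no rule at all.

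A second reply is that expansion would supply the data, since Table 1 puts 6 patients at the MTD. But the Synopsis says "The study design is a 3+3 Phase I dose escalation (N=3/cohort) with expansion at highest safe dose (N=6", and Section 1.1 says "If well tolerated at the MTD, an additional 6 patients will be studied to better define toxicity". Neither condition can be shown at a level where nobody has been treated, and expansion follows the declaration. The cohort summary (Section 6.2.2) and the data review at each level (Section 9.2) are review points that set no decision. The Synopsis remark on dose -1 concerns failure at 75 kBq/kg and means 50 kBq/kg.

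A third reply is that the branch is unlikely. This stands. Section 1.3.2 reports 50 kBq/kg in 541 phase III prostate cancer patients, with all-grade neutropenia 4% against 1% and platelet events 8% against 6%. Most hematologic DLTs here need grade 4 or bleeding, within 6 weeks. Transfer to osteosarcoma is uncertain: Section 5.1.1 admits platelets of 75,000/mm³ and ANC of 1,000/mm³, and required myeloid growth factor counts as a DLT. Still, nothing in the documents supports a rate as high as 20%. Nor is 25 kBq/kg unexplored in humans, since Section 4 cites a prostate cancer group of 29 at that dose.

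A reader might also bring in the expansion safety rule in Section 8.1: "Should DLTs occur in more than two patients at any time during the dose expansion phase clinical personnel and study investigators will meet". Exactly 2 DLTs in 6 would trigger no review, although 2 DLTs close a level in escalation. That threshold affects every expansion and is a separate matter. Within this branch it adds little. At 5% for both doses, exactly 2 of 6 has probability 15 × 0.05² × 0.95⁴ = 3.1%, so the joint chance is about 0.06% to 0.08% of trials. At 10% for both it is about 0.6% to 0.9%.

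**Conclusion.** The point holds as a gap in the rule for closure of the starting level, and it is minor. On two of the three routes that close 50 kBq/kg before escalation, no bullet opens 25 kBq/kg. Read literally, 25 kBq/kg becomes the MTD untested and without the plan's own six-patient confirmation. Read generously, it is a tentative MTD at a dose the plan does not list as assignable.

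The size is about 0.3% to 2.5% of trials at assumed DLT rates of 2% to 5%, and 6.6% to 8.7% at 10%, with half to all DLTs hematologic. These rates are assumptions, not figures from the plan.

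Two stronger conclusions are tempting and not supported. A reader might infer from the large share of closures that are uncovered that the fault is likely to occur; that share is conditional on a closure that is itself rare at plausible rates. A reader might also infer a hazard to patients; they would move to a lower dose, so what suffers is the dose conclusion.

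**What to change.** 1. Replace the level -1 bullet with: *If 50 kBq/kg is closed for 2 or more DLTs of any type (in the first 3 patients, or in 6 after 1/3) before any escalation to 75 kBq/kg, the next 3 patients are enrolled at level -1 (25 kBq/kg). If 0 or 1 of these 3 has a DLT, 3 more are enrolled at level -1, and 50 kBq/kg is not re-opened. Level -1 is the MTD only if fewer than 2 of 6 have a DLT; otherwise no MTD is declared.*
2. In both MTD bullets, make the prior level tentative whenever fewer than 6 patients, including none, have been treated there.
3. Add 25 kBq/kg to the dose lists in Sections 6.2.2 and 6.2.7, and use the assigned dose level in place of the fixed 50 kBq/kg in the Section 6.2.7 text and formula.

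The cost is a wording amendment. On this path the MTD is declared later, with at most 18 patients before replacements, within the stated 20.

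The new trigger is deliberately limited to closure before escalation. If 50 kBq/kg closes later, when patients are added there after a higher level has failed, testing 25 kBq/kg could need 3 + 6 + 3 + 6 + 6 = 24 patients, or 3 + 3 + 6 + 3 + 3 + 6 + 6 = 30 if 100 kBq/kg was opened first. Edit 2 would make 25 kBq/kg tentative there too, so that path needs its own decision on the total. It is outside this point, as are the Section 8.1 expansion threshold and the total of 15 (9 + 6) implied by Section 8.5.

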5.2 Withdrawal of subjects from study

5.2.1 Withdrawal

Subjects **must be withdrawn from the trial** (treatment and procedures) for the following reasons:

- Subject withdraws consent from study treatment and study procedures. A subject must be removed from the trial at his/her own request or at the request of his/her legally acceptable representative. At any time during the trial and without giving reasons, a subject may decline to participate further. The subject will not suffer any disadvantage as a result.
- Progressive disease and dose limiting toxicity (DLT)
- Subject is lost to follow-up.
- Death.

Subjects **may be** withdrawn from the study for the following reasons:

- The subject is non-compliant with study drug, trial procedures, or both; including the use of anti-cancer therapy not prescribed by the study protocol.
- Pregnancy. Pregnancy will be reported as an SAE. (Note: subjects who have been withdrawn from treatment with study drug because of pregnancy should not undergo CT scans [with contrast]/MRI or bone scans while pregnant.)
- If, in the investigator's opinion, continuation of the trial would be harmful to the subject's well-being.
- The development of a second cancer.
- Development of an intercurrent illness or situation which would, in the judgment of the investigator, significantly affect assessments of clinical status and trial endpoints.

- Deterioration of ECOG performance status to 4.
- Use of illicit drugs or other substances that may, in the opinion of the investigator, have a reasonable chance of contributing to toxicity or otherwise skewing trial result.

Any subject removed from the trial will remain under medical supervision until discharge or transfer is medically acceptable.

In all cases, the reason for withdrawal must be recorded in the CRF and in the subject's medical records.

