6.2.1 Radium-223 dichloride

6.2.2 Treatments to be administered

Ra-223 dichloride will be administered as a slow bolus IV injection at intervals of every 4 weeks for up to 6 cycles.

- Dose (50, 75, or 100 kBq/kg) will be assigned in cohorts of 3 after study registration in CORE.
- Dose #1 should be given within 30 days of study registration
- At least 3 patients will be required to successfully complete 6 weeks of therapy before advancing to the next cohort.
- Patients will receive the same Ra-223-dichloride dose as dose #1 for all subsequent doses.
- Monthly dosing (q 4 weeks +/- 6 days) as slow iv bolus for up to a total of 6 doses
- Monthly doses will be delayed, but no more than 2 weeks from scheduled dose for any grade 3 hematologic toxicity.

Criteria for subsequent doses (i.e. doses 2-6):

- Hematologic Toxicity (if present): Hb, ANC, and platelets- resolved to grade 2 or less within 6 weeks of prior dose. Since lymphopenia may be chronic, this will not be a criteria for subsequent doses
- All toxicities must be resolved to grade 2 or less in order to begin subsequent cycles
- Performance status ECOG 0 to 2
- Alkaline phosphatase stable or improving at the discretion of the treating physician
- Not on oxygen
- Not pregnant
- After dose #3 and before dose #4: stable disease or better in indicator lesions as determined by quantitative nuclear medicine imaging (^{18}F FDG PET-CT, quantitative $^{99\text{m}}\text{Tc}$ -MDP SPECT/CT, or Na^{18}F PET/CT) or RECIST criteria on anatomic imaging (note: often osteosarcoma "indeterminate" lesions 1-9 mm remain stable or have minimal change depending on chest CT technique).
- Anatomic imaging (CT or MRI) of all sites of disease along with chest CT at baseline and restaging for all patients will be done to allow for assessment of RECIST progression.
- RECIST progression will determine progressive disease regardless of other imaging.

For the Phase I aspect of the protocol, prior to advancing/changing dose levels, a cohort summary must be completed and submitted to the Clinical Research Monitor in the IND Office.

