If surgery is required, the patient should continue with study treatment, if this is considered safe in the treating Investigator's opinion. The surgeon needs to be notified that the patient has been given radioactive drug, and needs to follow the guidelines for radioactive protection.

Non-pathological fractures:

For traumatic fractures in weight-bearing bones during treatment phase, the study drug administration should be delayed for 2-4 weeks from the time of fracture.

Pathological fractures:

Pathological fractures may occur as the result of either progressive disease or increased physical activity associated with significant pain palliation. Pathologic fractures are to be treated in a manner that attempts to maintain the best functional status and quality of life. Study treatment may continue as planned.

Any Other Toxicity: Local practice will apply.

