7.1.1 Tabulated overview

Table 4 summarizes required labs and imaging.

Table 4: **Ra-223 dichloride for Osteosarcoma: observations/monitoring**

Test/Procedure	Before entry	Doses 2-6	After dose 3+ imaging	1 month after dose (end of study± 7 days)
-----------------------	---------------------	------------------	----------------------------------	---

Physical exam (including vital signs and performance status+BPS [§])	X	X		X
CT/MRI Scans ⁺	X		X	X
Nuclear Scans*	X		X	X
CBC** w diff	X	X	X	X
Creatinine	X		X	X
Bilirubin	X		X	X
ALT	X		X	X
Alk Phos	X	X	X	X
HCG**	X	X		
OSTEO ¹	X	X	X	X
BONE ALK ²	X	X	X	X
CTX ³	X	X	X	X
Pathology	X			

Nuclear scans: *bone scan required, Other imaging of indicator lesion(s): best study or studies for quantitative comparison after dose 3 and after dose 6 (e.g. LD of bone forming lesion on CT/MRI, or SUV on ¹⁸FDG-PET-CT, or SPECT with ^{99m}Tc-MDP bone scan, or Na¹⁸F PET).

[§]Brief Pain Survey.

⁺Evaluations to include anatomic imaging (CT or MRI) of all sites of disease along with chest CT at baseline and restaging for all patients will be done to allow for assessment of RECIST progression. RECIST progression will determine progressive disease regardless of other imaging.

HCG: Urine pregnancy test must be done within 7 days prior to start of study drug and when applicable prior to every cycle. Note serum HCG can be a false positive marker occasionally in osteosarcoma. For patients with a positive test result, pregnancy will be excluded by ultrasound.

**CBC w/diff: CBC every 2 weeks (± 7 days) for the first 2 cycles, then monthly or more frequently as clinically indicated

1 Osteoclastin

2 Bone specific alkaline phosphatase

3 Serum CTX

Timing of assessments

Assessments are to be done monthly as indicated in table 4.

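### Section 6.2.9 permits holding radium-223 and deferring other therapy at disease progression, where section 5.2.1 requires withdrawal

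*Combined protocol and SAP*

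**What the plan says.** Section 5.2.1 lists the reasons for which a subject must leave the trial, covering both treatment and procedures. One bullet reads "Progressive disease and dose limiting toxicity (DLT".

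Three other places agree with that rule:

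- Section 5.2.3 gives disease progression as an example of why a patient discontinues and may be replaced.
- Section 6.2.2 sets a condition for the fourth dose: "After dose #3 and before dose #4: stable disease or better in indicator lesions as determined by quantitative nuclear medicine imaging" (or by RECIST on anatomic imaging). It adds that RECIST progression decides progressive disease whatever other imaging shows.
- Section 8.1 treats RECIST growth of lung lesions as an off-study criterion.

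The dose-modification and escalation text within section 6.2.9 is different. It introduces a list of circumstances in which dosing may be delayed, and the first entry is disease progression. Under that entry: "The Investigator should delay cytotoxic chemotherapy, other systemic radioisotope, hemibody external radiotherapy or other investigational drug until the follow-up period". Then: "If such treatments have to be given during the treatment period, further study drug administrations must be discontinued". A last sentence lets progressing patients continue other treatment at the investigator's discretion. The entry does not say that progression itself ends study drug, and it does not refer to 5.2.1. Spinal cord compression appears further down the same list. It is to be treated and classed as disease progression, again with no instruction to stop or withdraw.

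**The concern.** The two sections attach different consequences to the same event. In 5.2.1 progression alone ends treatment. In 6.2.9 it is an occasion for a possible hold, and what ends treatment is the need for another systemic therapy. The dose-modification text also opens by urging every effort to give the full course, which leans towards holding rather than stopping. No rule says which section prevails, and section 11.1 asks for strict adherence to all of the protocol.

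What is at stake is patient management and consistent conduct. These patients have no standard curative option (section 5.1.1), and section 1.2 puts median survival after recurrence at about one year, so weeks spent waiting for other therapy matter. If some investigators withdraw and others hold, treatment duration and the post-progression alkaline phosphatase, imaging and toxicity data will also vary for reasons unrelated to dose.

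**Working it through.** There is no planned figure to reproduce. The check is a comparison of text, followed by simple schedule arithmetic.

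**1. The patient for whom the rules differ.** Take a patient with RECIST progression who does not need chemotherapy, another radioisotope, hemibody radiotherapy or another investigational drug at once.

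- Under 5.2.1: withdrawn. No dose remains to be delayed, and nothing makes other therapy wait.
- Under 6.2.9: the dose may be held, the listed therapies should wait for the follow-up period, and the trigger for stopping study drug has not been met.

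**2. When this can arise.** After baseline, imaging is scheduled at two points. The Table 4 footnote calls for the "best study or studies for quantitative comparison after dose 3 and after dose 6". Only the first of these precedes another dose, and there section 6.2.2 already requires stable disease or better. The remaining exposure is mainly progression found off schedule: on unscheduled imaging, or as spinal cord compression. The documents give no rate for either.

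**3. How long other therapy might be deferred.** The follow-up period is named only in the sentence quoted from 6.2.9, and its start is not defined. The final column of Table 4 is "1 month after dose (end of study± 7 days", and the table has no follow-up column.

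Doses are every 4 weeks, so with on-time dosing dose k falls at week 4(k − 1): weeks 0, 4, 8, 12, 16 and 20.

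- *If follow-up starts when study drug stops:* deferral is 0 weeks.
- *If the patient is kept on study until restaging and progression persists:* section 6.2.2 stops drug before dose 4, at about week 12. One month after dose 3 gives the same date, 8 + 4 = 12. Deferral from the visit for dose k is 12 − 4(k − 1):
  - dose 2 visit: 12 − 4 = 8 weeks
  - dose 3 visit: 12 − 8 = 4 weeks
- *If progression is found at the dose 5 or 6 visit,* no later restaging precedes a dose. Assuming follow-up starts at an end-of-study visit about 4 weeks after dose 6 (20 + 4 = week 24), deferral is 24 − 16 = 8 weeks or 24 − 20 = 4 weeks.

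These figures run from the named visit and assume no dose is held; a hold would push the dates back. An event found between visits is counted from its own date. All of them apply only if the investigator does not use the exception in 6.2.9 and start the other therapy.

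**The case against.** The strongest reply is that 5.2.1 is mandatory and the lead-in in 6.2.9 is permissive. No delay is ever required, and a patient taken off treatment can naturally be regarded as in follow-up, so withdrawing the patient satisfies both sections. The list is also a catch-all: it contains a discontinuation rule for prolonged grade 3 hematologic toxicity, continuation rules for surgery and pathological fracture, and the cord-compression classification. The progression entry can be read as a concomitant-therapy rule that fits the exclusion of concurrent anti-cancer treatment in section 5.1.2. Section 6.2.2 adds checks before each of doses 2 to 6: performance status, no oxygen, and alkaline phosphatase at the physician's discretion.

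Most of this stands, and it limits the point. It does not remove it, because nothing under the progression entry says that progression ends study drug.

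The 5.2.1 bullet might also be read as requiring progression and a DLT together. Neither alone would then mandate withdrawal, which sits badly with 5.2.3, 6.2.2 and 8.1. If that reading were intended, the text would still need correcting.

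Four stronger inferences are tempting, and the documents do not support them:

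- *The two rules cannot both be followed.* They can, by withdrawing the patient.
- *Other therapy could be deferred for up to 20 weeks.* This counts from the dose 2 visit to week 24 (24 − 4 = 20). It ignores the bar on dose 4 after progression at restaging.
- *The fracture rule is a second contradiction.* It says "Pathological fractures may occur as the result of either progressive disease or increased physical activity associated with significant pain palliation" and then "Study treatment may continue as planned". The second sentence is permissive and does not displace 5.2.1, and progressive disease is decided by RECIST. Stopping drug because a fracture is attributed to progression would add a subjective rule outside RECIST.
- *There is no follow-up.* Section 7.4.1 provides for adverse-event capture after the last dose, growth monitoring and survival reporting, and section 10 mentions post-study follow-up. What is missing is a defined start.

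**Conclusion.** The inconsistency is real and should be corrected. Section 6.2.9 as written allows study drug to be held and other systemic therapy postponed in a patient whom 5.2.1 removes from the trial. It is 6.2.9 that is out of line with the rest of the protocol.

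The size is modest. The main exposure is off-schedule progression, at an unknown frequency. Under the stated assumptions, deferral from the dose 2 or dose 3 visit is between 0 and about 8 or 4 weeks.

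A reader might infer damage to the dose-finding result, since 5.2.3 allows progressing patients to be replaced and holding rather than withdrawing could affect whether a cohort place is refilled. The documents do not show such an effect. DLTs are counted only in the first 6 weeks, scheduled restaging comes after dose 3, and replacement is left to the investigator.

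**What to change.** In the dose-modification text of section 6.2.9:

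1. Remove disease progression from the list of dosing-delay circumstances.
2. State that progressive disease (RECIST progression, or spinal cord compression as already classed there) ends study drug and leads to withdrawal under 5.2.1, after which other anticancer therapy may start at once.
3. Limit the advice to defer other anticancer therapy to patients without progression.

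Leave the pathological-fracture rule as it is. An optional note could say that 5.2.1 applies if progressive disease is documented. Splitting the 5.2.1 bullet into two separate reasons would remove the joint reading and is also optional.

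If treatment beyond progression is in fact intended, 5.2.1 must say so and define when it is allowed.

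The cost is a wording amendment, with no added visits, tests or patients.
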